3.5.2. Laboratory Data

Safety laboratory tests will be performed as described in the protocol. To determine if there are any clinically significant laboratory abnormalities, the haematological, clinical chemistry (serum) and urinalysis safety tests will be assessed against the criteria specified in the sponsor reporting standards. The assessment will not take into account whether each participant's baseline test result is within or outside the laboratory reference range for the particular laboratory parameter.

The baseline measurement is the predose measurement on Day -1.

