Physical Exam	X	X															
 • PE will be performed by trained medical personnel at the investigator site at Screening or Period 1 Day -1 only (height and weight must be obtained at Screening to obtain BMI for eligibility criteria). A brief PE may be performed at other designated time points at the discretion of the investigator.
Safety laboratory	X	X												X	X		
 • Safety laboratory assessments including urinalysis, hematology, and chemistry will be performed at Screening, Period 1 Day -1, Period 5 Day 4, and early termination/discontinuation if applicable. All the safety laboratory samples must be collected following at least a 4-hour fast. Additional safety laboratory assessments may be performed at any time at the discretion of the investigator.
FSH (postmenopausal women only)	X																
 • For confirmation of postmenopausal (amenorrheic for at least 12 consecutive months) female participants.
Urine drug testing	X	X															
 • Urine drug (mandatory) and alcohol breath test (at discretion of investigator) will be performed at Screening and on Period 1 Day -1. These tests may be performed at any other time at the discretion of the investigator.
Serology: HBsAg, HBsAb, HBcAb, HCVAb, and HIV	X																
 • HBsAb will be tested if HBsAg and/or HBcAb are positive.
Pregnancy test (WOCBP only)	X	X												X	X		

PFIZER CONFIDENTIAL

Table 1. Study Schedule of Assessment

Visit Identifier Abbreviations used in this table may be found in Appendix 10	Screening	Period 1				Period 2, 3 and 4				Period 5				F/U	E/T	Notes			
Days Relative to Day 1	Days -28 to -2	Day -1	1	2	3	4	1	2	3	4	1	2	3	4	28-35 Days				
Contraception check	X	X												X	X	X	
 • The investigator or his/her designee will discuss with the participant the need to use highly effective contraception consistently and correctly according to contraception guidelines (Appendix 4). 		
12-lead ECG (single)	X		X											X		X	
 • Single 12-lead ECG readings will be taken at specified time point. All ECG assessments will be made after at least a 5-minute rest in a supine position and prior to any blood draws or vital sign measurements. • The reading on Period 1 Day 1 will be done predose of Period 1 Day 1. 		

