4. STUDY DESIGN

4.1. Overall Design

This is a Phase 1, open-label, single dose, randomized, crossover study in healthy adult participants to estimate rBA of nirmatrelvir/ritonavir **CCI** [REDACTED] oral powder mixed with 3 different food vehicles (Test formulations) compared to the nirmatrelvir/ritonavir **CCI** [REDACTED] commercial tablets (Reference formulation) under fasted conditions, and to estimate the effect of food on the rBA of the nirmatrelvir/ritonavir oral powder formulation mixed with vanilla pudding. The study will also assess the safety, tolerability, and palatability of nirmatrelvir/ritonavir in healthy adult participants.

Approximately 12 adult healthy male and/or female participants will be enrolled and randomized to 1 of 6 possible treatment sequences. Participants who discontinue from the study for non safety reasons may be replaced at the sponsor's discretion in collaboration with the investigator. The replacement participant will receive the same treatment sequences as the participant who discontinued.

Each enrolled participant will participate in 5 study periods to receive 5 different treatments according to the sequence determined by randomization:

- Treatment A: Single oral dose of nirmatrelvir/ritonavir **CCI** [REDACTED] tablets under fasted condition
- Treatment B: Single oral dose of nirmatrelvir/ritonavir **CCI** [REDACTED] oral powder mixed in water under fasted condition
- Treatment C: Single oral dose of nirmatrelvir/ritonavir **CCI** [REDACTED] oral powder mixed in infant formula under fasted condition
- Treatment D: Single oral dose of nirmatrelvir/ritonavir **CCI** [REDACTED] oral powder mixed in vanilla pudding under fasted condition

- Treatment E: Single oral dose of nirmatrelvir/ritonavir **CCI** oral powder mixed in vanilla pudding under fed condition

Participants will be randomly assigned to 1 of 6 sequences as shown below in Table 3. Participants will be discharged on Day 4 of Period 5, following completion of all assessments. Between each treatment, a minimum of 4 days washout is proposed to minimize any residual nirmatrelvir concentrations prior to start of the next treatment. The total planned duration of participation from the Screening visit to the last follow-up phone call, is approximately 12 weeks.

Table 3. Randomized Treatment Sequences

Treatment Sequence	Period 1	Period 2	Period 3	Period 4	Period 5
Sequence 1 (N = 2)	Treatment A	Treatment B	Treatment C	Treatment D	Treatment E

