8. Screening supine BP ≥ 140 mm Hg (systolic) or ≥ 90 mm Hg (diastolic), following at least 5 minutes of supine rest. If BP is ≥ 140 mm Hg (systolic) or ≥ 90 mm Hg (diastolic), the BP should be repeated 2 more times and the average of the 3 BP values should be used to determine the participant's eligibility.
9. Baseline 12-lead ECG that demonstrates clinically relevant abnormalities that may affect participant safety or interpretation of study results (eg, baseline QTcF interval >450 msec, complete LBBB, signs of an acute, old or age indeterminate myocardial infarction, ST-T interval changes suggestive of myocardial ischemia, second- or third-degree AV block, or serious brady arrhythmias or tachyarrhythmias). If the baseline uncorrected QT interval is >450 msec, this interval should be rate -corrected using the Fridericia method and the resulting QTcF should be used for decision making and reporting. If QTcF exceeds 450 msec, or QRS exceeds 120 msec, the ECG should be repeated 2 more times and the average of the 3 QTcF or QRS values should be used to determine the participant's eligibility. Computer -interpreted ECGs

should be overread by a physician experienced in reading ECGs before excluding a participant.

10. Participants with **ANY** of the following abnormalities in clinical laboratory tests at Screening, as assessed by the study-specific laboratory and confirmed by a single repeat test, if deemed necessary:
 - AST **or** ALT level $\geq 1.5 \times$ ULN;
 - T bili level $\geq 1.5 \times$ ULN; participants with a history of Gilbert's syndrome may have direct bilirubin measured and would be eligible for this study provided the direct bilirubin level is \leq ULN.
 - eGFR < 60 mL/min/1.73 m² based on the CKD-EPI equation.

Other Exclusion Criteria:

11. History of alcohol abuse or binge drinking and/or any other illicit drug use or dependence within 6 months of Screening. Binge drinking is defined as a pattern of 5 (male) and 4 (female) or more alcoholic drinks in about 2 hours. As a general rule, alcohol intake should not exceed 14 units per week (1 unit = 8 ounces (240 mL) beer, 1 ounce (30 mL) of 40% spirit or 3 ounces (90 mL) of wine).
12. Use of tobacco or nicotine containing products in excess of the equivalents of 5 cigarettes per day or 2 chews of tobacco per day.
13. Blood donation (excluding plasma donations) of approximately 1 pint (500 mL) or more within 60 days prior to dosing.

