2.2. Study Objectives and Endpoints

Objectives	Endpoints
Primary:	Primary:

 To estimate the rBA of the nirmatrelvir/ritonavir [REDACTED] oral powder mixed with water compared to the nirmatrelvir/ritonavir [REDACTED] [REDACTED] commercial tablets under fasted conditions. 	
 The test/reference ratios for AUC_{inf} (if data permits), AUC_{last}, and C_{max} of nirmatrelvir and ritonavir.

Objectives	Endpoints

 • To estimate the rBA of the nirmatrelvir/ritonavir [REDACTED] oral powder mixed with infant formula compared to the nirmatrelvir/ritonavir [REDACTED] commercial tablets under fasted conditions. • To estimate the rBA of the nirmatrelvir/ritonavir [REDACTED] oral powder mixed with vanilla pudding compared to the nirmatrelvir/ritonavir [REDACTED] commercial tablets under fasted conditions. • To estimate the rBA of the nirmatrelvir/ritonavir [REDACTED] oral powder mixed with vanilla pudding under fed conditions compared to the nirmatrelvir/ritonavir [REDACTED] commercial tablets under fasted conditions. 	
Secondary:	Secondary:

 • To estimate the effect of food on the rBA of the nirmatrelvir/ritonavir [REDACTED] oral powder mixed with vanilla pudding. • To evaluate the safety and tolerability of nirmatrelvir/ritonavir in healthy participants. • To assess the palatability of nirmatrelvir/ritonavir oral powder mixed with water/ infant formula/ vanilla pudding. 	
 • The test/reference ratios for AUC_{inf} (if data permits), AUC_{last}, and C_{max} of nirmatrelvir and ritonavir. • Assessment of TEAEs, clinical laboratory abnormalities, vital signs, PEs, and 12 lead ECGs. • Assessment of palatability via questionnaire: mouth feel, bitterness, tongue/mouth burn, throat burn and overall liking.
[REDACTED]	[REDACTED]
[REDACTED]	[REDACTED]

Objectives	Endpoints
CCI [REDACTED]	[REDACTED]

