6.6.2. Laboratory Data

Laboratory data will be listed and summarized by treatment in accordance with the CaPS.

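### SAP 3.5.2 counts a laboratory abnormality carried over from Day -1 the same as a new one, in a trial with no untreated period

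*SAP*

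**What the plan says.** SAP 3.5.2 says that hematology, chemistry and urinalysis results "will be assessed against the criteria specified in the sponsor reporting standards". It adds: "The assessment will not take into account whether each participant's baseline test result is within or outside the laboratory reference range". The same section then defines a baseline: "The baseline measurement is the predose measurement on Day -1".

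The planned output is in SAP 6.6.2: "Laboratory data will be listed and summarized by treatment in accordance with the CaPS". The visible text names no shift table, no change-from-baseline summary and no split by baseline status. Neither the sponsor criteria nor the CaPS standard is reproduced in the protocol or SAP.

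Laboratory abnormalities belong to a secondary endpoint, listed in SAP 2.2 as "Assessment of TEAEs, clinical laboratory abnormalities, vital signs, PEs, and 12 lead ECGs". The schedule of activities (Protocol 1.3) says that the safety laboratory tests "will be performed at Screening, Period 1 Day -1, Period 5 Day 4, and early termination/discontinuation if applicable". On treatment, Protocol 4.1 says: "Each enrolled participant will participate in 5 study periods to receive 5 different treatments". All five contain nirmatrelvir/ritonavir.

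**The concern.** A table of laboratory abnormalities in a single-dose crossover is read as a description of what happened after dosing. With no placebo or untreated period, the trial has no concurrent estimate of the background rate. Only each participant's own predose value can separate a finding that was already there from one that arose after dosing. The stated rule leaves the reference-range status of that value out of the count.

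The sampling schedule sharpens the point. There is one scheduled postdose laboratory sample, and it follows whichever treatment was given in Period 5. A by-treatment summary will therefore place a carried-over abnormality under D or E. Treatments A, B and C have no scheduled postdose laboratory data to set beside it. What is at stake is how a small descriptive safety table is read. The primary pharmacokinetic ratios are untouched.

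**Working it through.** The documents give no count or rate of laboratory abnormalities, so there is no plan figure to reproduce. The check has three parts.

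**1. Which abnormalities the rule counts**

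- Scheduled samples (Protocol 1.3): Screening and Period 1 Day -1 before dosing; Period 5 Day 4 after dosing. An early-termination sample is added where it applies.
- Rule (SAP 3.5.2): results are compared with the sponsor criteria, without regard to whether baseline was inside or outside the reference range.
- It follows that a participant who is abnormal on Day -1 and still meets the criterion on Period 5 Day 4 is counted in the same way as a participant who was normal on Day -1.

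**2. Weight of one carried-over case**

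- Planned size (Protocol 4.1): 12 participants, 2 in each of 6 sequences.
- Period 5 treatment (Protocol Table 3): Sequences 1 to 3 end with E and Sequences 4 to 6 end with D, so 3 × 2 = 6 participants for each.
- Overall: 1/12 = 8.3%.
- By treatment, if the Period 5 Day 4 sample is attributed to the Period 5 treatment: 1/6 = 16.7%.

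**3. How many such cases might occur (illustration only)**

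Tests counted from Protocol Table 5: 13 hematology + 15 chemistry + cystatin C + 7 urinalysis = 36.

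Let q be the chance that a given test already meets its criterion before dosing. Let s be the chance that it still does, or does again, on Period 5 Day 4. Neither is in the documents. Assume that the tests are independent and share the same q.

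- Chance that a participant has at least one carried-over abnormality: P = 1 − (1 − q·s)^36
- Expected participants of 12: 12·P
- Chance of at least one such participant: 1 − (1 − P)^12

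With s = 0.5:

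| q | 12·P | Chance of at least one of 12 |
|---|---|---|
| 0.1% | 0.2 | 19% |
| 0.5% | 1.0 | 66% |
| 1% | 2.0 | 88% |
| 2.5% | 4.4 | 99.6% |

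For example, at q = 1%: P = 1 − 0.995^36 = 0.165, and 12 × 0.165 = 2.0.

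With s from 0.25 to 0.9, the expected number runs from 0.1 to 0.4 at q = 0.1% and from 2.4 to 6.7 at q = 2.5%. The result depends mainly on q, which is unknown.

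Independence pushes these figures up. Related tests (hemoglobin with hematocrit and red cell count, AST with ALT) tend to be abnormal together, so for a given q fewer participants would have at least one abnormality.

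**The case against.** The strongest reply is that the rule is disclosed, prespecified and descriptive. No hypothesis is tested, and the endpoint is worded as laboratory abnormalities, not treatment-emergent ones. Counting without regard to baseline tends to over-report and cannot hide an abnormality. Laboratory data are also listed, so with 12 participants and one scheduled postdose sample the two values can be compared by eye. Adverse event status is judged separately under Protocol 10.3.1, where worsening from baseline is named and stable pre-existing conditions are excluded. All of this is correct, and it keeps the point small. It does not correct the summary table, which is a different output from the listings and the adverse event tables.

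Three stronger readings are tempting, and the documents do not support them.

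- A reader might infer that every predose abnormality is reported as a study finding. The SAP does not say that predose results are counted. Only an abnormality that persists or recurs after dosing is shown to be counted; one that has resolved by Period 5 Day 4 is not.
- A reader might infer from the entry criteria that participants who already meet a sponsor criterion will be enrolled. Protocol 5.2 criterion 10 does admit AST or ALT above the upper limit of normal but below 1.5 times it. It also says that a participant with a history of Gilbert's syndrome "would be eligible for this study provided the direct bilirubin level is" not above the upper limit. Such values may lie outside the reference range, but the sponsor thresholds are not given, so they are not shown to meet a criterion.
- A reader might infer that baseline is unused altogether. SAP 3.5.2 sets aside reference-range status only. A sponsor criterion could itself use the baseline value, and CaPS could already produce a baseline-aware table. Neither can be checked from the documents.

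**Conclusion.** The point holds in a limited form. As written, SAP 3.5.2 makes a carried-over abnormality indistinguishable from a new one in the summary count, and this design offers no comparator other than Day -1. One such case is worth 8.3 points overall, or about 16.7 points under D or E. The second figure assumes full enrolment and completion, and attribution of the last sample to the Period 5 treatment.

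The number of cases cannot be derived from the documents. The range of about 0.2 to 4.4 of 12 rests on assumed predose rates, half persisting, and 36 independent tests with equal rates. It should not be quoted as a prediction. The prevalence of abnormalities before dosing would be the wrong measure, since only those met again after dosing reach the postdose count.

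This is a low-cost improvement to a descriptive secondary safety summary. It is not a flaw in the primary analysis.

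**What to change.** Keep the planned table without regard to baseline. Beside it, add one of the following:

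- a count of each abnormality split by Day -1 status (sponsor criterion not met on Day -1, or already met); or
- a shift table from Day -1 to the postdose sample.

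In the listing, show the Day -1 value next to each flagged result. Report participants who already met the criterion on Day -1 separately, with both values. Do not reclassify them by a rule that counts any value worse than Day -1: without a threshold, ordinary assay variation in someone already abnormal would be labelled as new.

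If CaPS already generates such an output, it is enough for SAP 6.6.2 to name it.

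The cost is a sentence or so in the SAP, one extra table or column, and minor programming. No new data are needed, because the Day -1 and Period 5 Day 4 samples are already scheduled.

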3.5.3. Vital Signs

Supine blood pressure (BP) and pulse rate (PR) will be measured at times specified in the SoA given in the protocol.

For each period, the baseline measurement is the predose measurement on Day 1.

3.5.4. Electrocardiograms

QT interval, QTcF, PR, QRS and heart rate (HR) will be recorded at each assessment time indicated in the SoA given in the protocol. QTcF will be derived using Fridericia's heart rate correction formula:

OTcF = OT / (RR)^(1/3) where RR = 60/HR (if not provided)

The baseline measurement is the predose measurement on Period 1 Day 1.

4. ANALYSIS SETS (POPULATIONS FOR ANALYSIS)

Data for all participants will be assessed to determine if participants meet the criteria for inclusion in each analysis population prior to releasing the database and classifications will be documented per standard operating procedures.

PFIZER CONFIDENTIAL

Participant Analysis Set	Description
Enrolled/Randomly assigned to study intervention	“Enrolled” means a participant's agreement to participate in a clinical study following completion of the informed consent process and screening. Potential participants who are screened for the purpose of determining eligibility for the study, but do not participate in the study, are not considered enrolled, unless otherwise specified by the protocol. A participant will be considered enrolled if the informed consent is not withdrawn prior to participating in any study activity after screening.
Safety Analysis Set	All participants who take at least 1 dose of study intervention. Participants will be analyzed according to the product they actually received.
PK Concentration Set	All participants who take at least 1 dose of study intervention and in whom at least 1 concentration value is reported.
PK Parameter Set	All participants who take at least 1 dose of study intervention and in whom at least 1 of the PK parameters of primary interest are reported.

5. GENERAL METHODOLOGY AND CONVENTIONS

Final analysis will be performed after study participant data set release following last participant last visit.

5.1. Hypotheses and Decision Rules

No statistical hypothesis will be tested in this study.

5.2. General Methods

5.2.1. Analyses for Binary/Categorical Endpoints

For binary or categorical variables, number of participants, numbers and percentages of participants meeting the categorical criteria will be presented in accordance with the Clinical Data Interchange Standards Consortium and Pfizer Standards (CaPS).

5.2.2. Analyses for Continuous Endpoints

For continuous variables, the data will be summarized using the number of participants, mean, median, standard deviation (SD), minimum, and maximum in accordance with the CaPS. For appropriate PK parameters, geometric mean and geometric coefficient of variation (%CV) will also be summarized.

5.3. Methods to Manage Missing Data

5.3.1. Pharmacokinetic Data

Methods to handle missing PK data are described below.

Concentrations Below the Limit of Quantification:

In all data presentations (except listings), concentrations below the limit of quantification (BLQ) will be set to zero. (In listings BLQ values will be reported as “<LLQ”, where LLQ will be replaced with the value for the lower limit of quantification.).

Deviations, Missing Concentrations and Anomalous Values:

In summary tables and plots of median profiles, statistics will be calculated having set concentrations to missing if 1 of the following cases is true:

1. A concentration has been collected as ND (ie, not done) or NS (ie, no sample).
2. A deviation in sampling time is of sufficient concern or a concentration has been flagged anomalous by the pharmacokineticist.

Note that summary statistics will not be presented at a particular time point if more than 50% of the data are missing.

An anomalous concentration value is one that, after verification of bioanalytical validity, is grossly inconsistent with other concentration data from the same individual or from other participants. For example, a BLQ concentration that is between quantifiable values from the same dose is considered as anomalous. Anomalous concentration values may be excluded from PK analysis at the discretion of the PK analyst.

PK Parameters:

Actual PK sampling times will be used in the derivation of PK parameters. If a PK parameter cannot be derived from a participant's concentration data, the parameter will be coded as NC (ie, not calculated). (Note that NC values will not be generated beyond the day that a participant discontinues).

In summary tables, statistics will not be presented for a particular treatment group if more than 50% of the data are NC. For statistical analyses, PK parameters coded as NC will also be set to missing.

If an individual participant has a known biased estimate of a PK parameter (due for example to dosing error or an unexpected event such as vomiting before all the compound is adequately absorbed from the gastrointestinal tract), this will be footnoted in summary tables and will not be included in the calculation of summary statistics or statistical analyses. For instance, if a participant has a vomiting event post dose that is within a duration of time that is 2-times the derived median T_{max} for the population for the administered treatment, then the

pharmacokineticist should consider the exclusion of the PK concentration data collected following the initial vomiting event in that treatment period and the PK parameter data reported for that treatment period from the datasets used to calculate summary statistics or statistical analyses.

5.3.2. Safety Data

Missing values in standard summaries of AEs, laboratory data, vital signs, and ECGs will be imputed according to CaPS.

6. ANALYSES AND SUMMARIES

6.1. Primary Endpoints

For the estimation of rBA of nirmatrelvir/ritonavir oral powder in 3 different food delivery vehicles relative to the nirmatrelvir/ritonavir commercial tablets, *natural log transformed AUC_{inf} (if data permits), AUC_{last} and C_{max} will be analyzed using a mixed effect model with sequence, period and treatment as fixed effects and participant within a sequence as a random effect. Estimates of the adjusted mean differences (Test-Reference) and corresponding 90% confidence intervals will be obtained from the model. The adjusted mean differences and 90% confidence intervals for the differences will be exponentiated to provide estimates of the ratio of adjusted geometric means (Test/Reference) and 90% confidence intervals for the ratios. Treatment A will be the Reference treatment while Treatments B, C, D and E will be the Test treatments.*

Residuals from the models will be examined for normality and the presence of outliers via visual inspection of plots of residuals vs predicted values and normal probability plots of residuals but these will not be included in the CSR. If there are major deviations from normality or outliers then the effect of these on the conclusions will be investigated through alternative transformations and/or analyses excluding outliers. Justification for any alternative to the planned analysis will be given in the report of the study.

[figure not shown]
